7.2.1. Primary Analysis

The primary objective of this study is to evaluate change from Baseline in liver Cu concentration following treatment with ALXN1840 at Week 48 in patients with WD. The primary analysis will be performed using the FA Set in the Treatment Period.

To assess the reduction in liver Cu concentration, liver biopsies will be taken during the Screening Period and at Week 48 of Treatment Period, where the assessment from Screening will be regarded as Baseline. The change from Baseline in liver Cu concentration will be evaluated using a paired sample t-test on Baseline and Week 48 assessment values.

Prior to the primary analysis, multiple imputation will be used to impute missing data at Week 48 due to any reason based on Baseline values. Missing values at Week 48 will be imputed 20 times via SAS PROC MI, using the MCMC method, including Baseline and Week 48 liver Cu assessment values. A paired sample t-test analysis will be applied for each of the 20 imputed datasets, and then 20 sets of analysis results will be combined afterward via SAS PROC MIANALYZE. The combined estimate of the treatment effect, standard error (SE), 95% CI, and p-value will be summarized.

7.2.1.1. Handling of Dropouts or Missing Data

For missing liver Cu concentration data at Week 48, the multiple imputation method will be used for the primary analysis and sensitivity analysis. Details for multiple imputation can be referred to in Section 7.2.1, and an example of SAS code can be referred to in Section 9.5. The Baseline value carried forward method will also be used in the second sensitivity analyses, where missing Week 48 values will be imputed to Baseline values.

Note: Liver Cu concentrations reported as < LLOQ or > ULOQ will be considered non-evaluable. Non-evaluable data will be excluded when deriving summary statistics in both liver Cu primary analysis and Cu sensitivity analysis. This same principle will also be applied to the analysis of other live metals.

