9.3. Populations for Analyses

For purposes of analysis, the following populations are defined in Table 7.

Table 7: Populations for Analyses

Population	Description
Enrolled	All patients who sign the informed consent form
Safety Analysis Set in Treatment Period	All patients who receive at least 1 dose of treatment in the Treatment Period
Full Analysis Set in Treatment Period	All patients who receive at least 1 dose of treatment in the Treatment Period and have at least baseline liver Cu value
Per Protocol Set in Treatment Period	All patients who receive at least 1 dose of treatment in the Treatment Period and have both baseline and Week 48 liver Cu values. Patients with major protocol deviations that are likely to impact the primary efficacy endpoint analysis will be excluded from the Per Protocol Set. Major protocol deviations, and the Per Protocol Set, will be defined, documented, and agreed within Alexion prior to database lock.
Safety Analysis Set in Extension Period	All patients who receive at least 1 dose of ALXN1840 in the Extension Period
Full Analysis Set in Extension Period	All patients who receive at least 1 dose of ALXN1840 in the Extension Period and have at least baseline liver Cu value

Abbreviation: Cu = copper.

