6.2.2. Full Analysis (FA) Set in the Treatment Period

The Full Analysis (FA) Set in the Treatment Period is defined as all patients who receive at least 1 dose of study drug in the Treatment Period and have at least a Baseline liver Cu value evaluable. This population will be used for the primary, secondary, and exploratory efficacy analyses.

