6.2.3. Per Protocol (PP) Set in the Treatment Period

The Per Protocol (PP) Set in the Treatment Period is defined as all patients who receive at least 1 dose of study drug in the Treatment Period and have both Baseline and Week 48 liver Cu values evaluable. Patients with important protocol deviations that are likely to impact the primary efficacy endpoint analysis will be excluded from the PP Set. Important protocol deviations and the PP Set will be defined, documented, and agreed within Alexion prior to database lock. This population will be used for the sensitivity analyses for the primary endpoint.

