6.3.2. Full Analysis (FA) Set in the Extension Period

The FA Set in the Extension Period is defined as all patients who receive at least 1 dose of ALXN1840 in the Extension Period and have at least a Baseline liver Cu value evaluable. This population will be used for the efficacy analyses in the Extension Period.

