7.2. Efficacy Analyses

All efficacy analyses and summaries will be based on the FA Set in the Treatment Period. Additionally, the primary analysis will be performed on the PP Set in the Treatment Period. A 2-sided Type I error rate of 0.05 will be used to define statistical significance for all endpoints

without adjusting for multiplicity. Sample SAS code for the following analyses can be found in Section 9.5.

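### SAP 7.2.1.1 discards liver copper results for being outside the assay range, and no planned analysis keeps them, so the effect of losing out-of-range Baselines on the primary estimate is never estimated

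*SAP*

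**What the plan says.** The note in SAP 7.2.1.1 reads: "Liver Cu concentrations reported as < LLOQ or > ULOQ will be considered non-evaluable". It goes on: "Non-evaluable data will be excluded when deriving summary statistics in both liver Cu primary analysis and Cu sensitivity analysis". The only criterion is the position of the result relative to the assay limits.

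The word evaluable then decides who is analysed:

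- **Treatment Period FA Set (SAP 6.2.2):** patients must "have at least a Baseline liver Cu value evaluable".
- **Efficacy analyses (SAP 7.2):** "All efficacy analyses and summaries will be based on the FA Set in the Treatment Period".
- **Per Protocol (PP) Set (SAP 6.2.3):** patients must "have both Baseline and Week 48 liver Cu values evaluable".
- **Extension FA Set (SAP 6.3.2):** patients must "have at least a Baseline liver Cu value evaluable. This population will be used for the efficacy analyses in the Extension Period".

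Table 7 in Protocol 9.3 asks only that FA Set patients "have at least baseline liver Cu value". SAP 4.2 records both the added word evaluable and the note on the limits, and gives clarification as the reason for each. SAP 4.1, which lists departures from the protocol's analyses, mentions neither.

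For the primary analysis, SAP 7.2.1 states that "multiple imputation will be used to impute missing data at Week 48 due to any reason based on Baseline values". SAP 7.2.1.5 plans three sensitivity analyses: Baseline carried forward, observed pairs, and the PP Set.

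**The concern.** A result below or above the assay range is not absent. It tells us that the concentration is low or high. Removing it makes inclusion depend on the size of the primary outcome.

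**At Baseline** the loss is complete. The patient leaves the FA Set, nothing restores the value, and the primary, secondary and exploratory efficacy analyses all lose that patient. A Baseline above the upper limit belongs to a patient with the most liver copper, who may have the largest absolute fall. A Baseline below the lower limit works the other way.

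**At Week 48** the text leaves two readings open. The value may count as missing and be imputed, or the patient's pair may simply be left out. The second reading is close to the observed-pairs analysis, so both estimates would be available. If the value does count as missing, carrying Baseline forward scores a patient who fell below the lower limit as having no change.

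**The sensitivity analyses share the restriction.** All three start from in-range Baselines. The PP Set holds only patients with in-range values at both visits, so it has nothing to impute and differs from the observed-pairs analysis only through important protocol deviations. Agreement among the planned analyses therefore says nothing about lost Baselines.

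**Working it through.** **1. The plan's own figure.** Protocol 9.2 and SAP 9.3 give n = 24, a reduction of 228, SD of the paired difference 319, one-sided 0.025 and power 92%. The noncentrality is 228/319 × √24 = 3.50, with 23 degrees of freedom and critical value 2.069. The noncentral t distribution gives 91.8%, which reproduces 92%. The standard error of the mean change is 319/√24 = 65.

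**2. Inputs for the illustration.** From Protocol 9.2: Baseline mean 570, Week 48 mean 342 and SD of difference 319. Assumed, because the documents do not give them: lognormal values, CVs of 0.5 to 0.8 at each visit in steps of 0.1 (16 pairs), and the assay limits. The correlation is solved so that the SD of the difference is 319.

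**3. One case by hand: both CVs 0.6, upper limit 1200.**

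- SDs: 570 × 0.6 = 342 and 342 × 0.6 = 205.2.
- Correlation: (342² + 205.2² − 319²)/(2 × 342 × 205.2) = 0.408. On the log scale: ln(1 + 0.408 × 0.36)/ln(1.36) = 0.446.
- Log SD: √ln(1.36) = 0.5545. Log mean at Baseline: ln 570 − 0.1537 = 6.192.
- z = (ln 1200 − 6.192)/0.5545 = 1.620, and Φ(z) = 0.947, so 5.3% of Baselines are lost.
- Mean Baseline among those kept: 570 × Φ(1.620 − 0.5545)/0.947 = 570 × 0.857/0.947 = 515.
- Their mean at Week 48: 342 × Φ(1.620 − 0.446 × 0.5545)/0.947 = 342 × 0.915/0.947 = 330.
- Mean change among those kept: 330 − 515 = -185, against -228 in all patients.

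Simulating the planned analyses for this case gives -189 (imputed), -188 (observed pairs) and -187 (carried forward). They agree with one another, and all fall about 40 short.

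**4. All 16 CV pairs**, by simulation with 2 million patients each. Imputed means that an out-of-range Week 48 value is replaced by its regression on Baseline among in-range pairs. Kept at limit means that all patients stay and both visits are set to the limit. Spread is the largest minus the smallest of the three planned ways of handling Week 48. The true change is -228.

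| Assumed limit | Imputed | Observed pairs | Carried forward | Spread | Kept at limit |
|---|---|---|---|---|---|
| LLOQ 50 | -226 to -228 | -227 to -229 | -225 to -228 | 0–2 | -228 |
| LLOQ 100 | -209 to -232 | -220 to -240 | -202 to -233 | 1–18 | -226 to -228 |
| LLOQ 150 | -178 to -242 | -203 to -257 | -161 to -243 | 7–44 | -219 to -229 |
| ULOQ 1200 | -159 to -221 | -159 to -220 | -159 to -217 | 0–5 | -187 to -225 |

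**5. Which visit drives it.** At a ULOQ of 1200, 3.5–7.9% of Baselines are out of range (1.0 to 2.2 of 28 patients). The imputed estimate falls short of 228 in all 16 pairs, by 7 to 69. At LLOQ 100, 0.0–1.7% of Baselines are lost, and losing them alone moves the mean only to about -228 to -232. At LLOQ 150 the figures are 0.5–6.1% and -229 to -244. Most of the LLOQ effect therefore comes from Week 48, where 0.9–8.1% (LLOQ 100) or 6.5–20.6% (LLOQ 150) are out of range. There the spread column shows that the planned analyses partly reveal it. The direction also varies: at LLOQ 150 the imputed estimate is too small in 13 pairs and too large in 3.

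**6. Power.** If the effect and SD are unchanged, losing 1 or 2 of 24 patients lowers power from 91.8% to 90.6% or 89.2%. The issue is the estimate rather than power.

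**The case against.** The strongest reply is that nobody can show from these documents that any result will be out of range. The limits and CVs in the calculation are assumptions, and with a wide enough assay range the note never operates. That stands, and it limits the claim to a gap in the plan. The largest illustrated shift, 69, is also about one standard error (65). At a ULOQ it works against the drug in this model. If every patient fell by the same amount whatever their Baseline, losing Baselines would cost power but cause no bias.

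Four stronger readings are tempting and should not be drawn:

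- **The primary result is biased in a known direction.** Upper and lower limits pull in opposite ways, and neither limit is given. A spurious fall from regression to the mean can be constructed, 24 to 66 units with no true effect, but only by removing the lowest 10–20% of Baselines. That is more than the 6.1% maximum in the table's scenarios.
- **The change was concealed.** SAP 4.2 records both edits. Protocol 9.4 already required a valid Baseline value, and Protocol 9.2 sized the trial for evaluable patients. Neither passage equates out of range with invalid, however, so Table 7 was still narrowed without an entry in SAP 4.1.
- **Nobody will know who was lost.** SAP 7.1.2 plans a listing of reasons for exclusion from efficacy analyses. It will identify the patients but give no alternative estimate.
- **Carrying Baseline forward always scores a result below the LLOQ as no change.** That holds only if the value counts as missing, which SAP 7.2.1.1 does not say.

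**Conclusion.** The concern holds as a gap in the sensitivity analyses and in the wording. SAP 7.2.1.1 makes a stated, outcome-dependent exclusion. Through SAP 6.2.2 and 7.2 it removes patients with out-of-range Baselines from all Treatment Period efficacy analyses, and through SAP 6.3.2 from the Extension FA Set. No planned analysis keeps them. The handling of a non-evaluable Week 48 value is not settled.

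The size cannot be determined from the documents and may be zero. Under the lognormal assumptions above, the clearest risk is an upper limit near 1200: the estimate could be 7 to 69 units short of 228 while the planned analyses agree to within 5. A lower limit of 50 would have almost no effect.

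A reader might infer that the primary rule must be replaced by substitution at the limit. The documents do not compel that, and substitution has its own bias: at a ULOQ of 1200 it still leaves the estimate 3 to 41 short. The point is worth fixing because the remedy is cheap and, with about 24 evaluable patients, one or two extreme values can move a mean.

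**What to change.** Leave the primary rule in place if preferred, and make four changes to the SAP:

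1. **SAP 7.2.1.5:** add one sensitivity analysis. Suggested text: *The primary analysis will be repeated in all patients who received at least one dose of study drug and have a Baseline liver Cu result, including results reported as below the LLOQ or above the ULOQ. Out-of-range results at either visit will be retained at the reported limit (or treated as censored). Week 48 results that were not obtained will be handled as in Section 7.2.1.*
2. **SAP 7.2.1.1:** state whether a non-evaluable Week 48 value is treated as missing under SAP 7.2.1 or left out.
3. State the LLOQ and ULOQ of the liver copper assay.
4. Report the number of results below the LLOQ and above the ULOQ by visit.

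There is a partial precedent. SAP 7.2.5.2 sets PD and biomarker values below the LLOQ to the LLOQ in FA Set summaries, although it has no rule for values above the ULOQ and uses 0 or missing in other settings.

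The cost is one extra analysis and some wording, with no new data collection beyond the laboratory's limits. Neither version is perfect. Substitution at an upper limit removes only part of the bias, and a censored model depends on a distribution that about 24 patients can hardly check. Either is adequate for showing whether the discarded results matter.

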7.2.1.2. Subgroup Analyses

Subgroup analyses are considered unnecessary. Additional subgroup analyses may be performed post-hoc, as appropriate.

7.2.1.3. Multicenter Studies

This is a multicenter study. Efficacy data collected from all study centers will be pooled for data analysis.

7.2.1.4. Hypothesis Testing and Significance Level

The hypothesis to be tested for the primary endpoint is as follows:

$$H_0: \mu_{\text{ALXN1840}} \geq 0 \text{ versus } H_1: \mu_{\text{ALXN1840}} < 0$$

where μ_{ALXN1840} is the mean change from Baseline in liver Cu concentration ($\mu\text{g Cu/g dry liver}$) at Week 48. A 2-sided Type I error rate of 0.05 will be used to define statistical significance without adjusting for multiplicity.

7.2.1.5. Sensitivity Analyses

Three sensitivity analyses will be performed to assess the robustness of the analysis result, as follows:

- Similar to the primary analysis but use Baseline value carried forward to impute missing Week 48 data instead
- Similar to the primary analysis but use the observed data from patients where both Baseline and Week 48 data are available instead
- Similar to the primary analysis but use the PP Set in the Treatment Period instead

7.2.2. Secondary Analyses

All secondary analyses will be performed using the FA Set in the Treatment Period.

Histologic assessments (steatosis, inflammation, and fibrosis) and CGI-S will be summarized for Baseline Visit and post-baseline visits using descriptive statistics. Change from Baseline will also be summarized for each post-baseline visits. Since CGI-I is only collected post-dose, only post-baseline visits will be summarized. In addition, the following analysis will be done.

The CGI-S data will be analyzed using MMRM. In the MMRM model, the response variables will be change from Baseline. Visit and Baseline values will be used as covariates. The restricted maximum likelihood (REML) estimation will be used. An unstructured covariance matrix will be used to model the within-subject error and the Kenward-Roger approximation will be used to estimate the degrees of freedom. If the fit of the unstructured covariance structure fails to converge or a positive definite Hessian matrix is not produced, the following covariance structures will be tried in order until convergence is reached: Toeplitz with heterogeneity, autoregressive with heterogeneity, Toeplitz, autoregressive, and compound symmetry. Based on the model, the comparison of post-baseline versus Baseline time points will be tested using a 2-sided test at the $\alpha = 0.05$ level of significance. The least squares mean (LSM) change from Baseline and associated SE will also be presented along with the 95% CI. The reference SAS code for the MMRM model can be found in Section 9.5.

Mean and 95% CI of CGI-S will be plotted over time. Additionally, patient level data over time will be plotted by spaghetti plot.

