9.4.1. Efficacy Analyses

9.4.1.1. Treatment Period

The primary objective of this study is to evaluate change in liver Cu concentration following treatment with ALXN1840 at 48 weeks in patients with WD. The primary analysis will be performed using the Full Analysis Set in the Treatment Period.

The change in liver Cu concentration will be evaluated using a paired samples t-test. For the primary analysis, a multiple imputation method will be used for missing data imputation.

Missing values for each patient will be imputed multiple times based on the estimated means from patients with similar baseline liver Cu concentration values. This approach will be used for all missing data at Week 48 due to any reason including, but not limited to, loss to follow-up and withdrawal of consent. The details of implementing this multiple imputation approach are as follows:

- Step 1: Missing values at Week 48 will be imputed 20 times via SAS PROC MI, using MCMC statement, including baseline and Week 48 liver Cu value; imputed values at Week 48 will be retained in the imputed datasets.
- Step 2: Apply paired samples t-test analysis for each of the 20 imputed datasets and save the mean and standard error at Week 48 from each of the 20 analyses.
- Step 3: Combine the 20 sets of analysis results via SAS PROC MIANALYZE. The combined treatment effect, confidence interval, and p-value will be estimated.

Sensitivity analyses will be performed to assess the robustness of the analysis result and will include:

- Use baseline value carried forward to impute missing Week 48 data
- Analyze primary endpoint using the Per Protocol Set, multiple imputation will be used to impute missing Week 48 data

Secondary and exploratory analyses will be performed using the Full Analysis Set in the Treatment Period.

For continuous endpoints that are measured multiple times between baseline and Week 48, data will be analyzed using mixed model repeated measures (MMRM) analysis. Fixed-effect terms will include visit and baseline value as covariates. An unstructured covariance will be used to model within-patient error.

For exploratory endpoints, data will be analyzed as observed, for endpoints that are only measured at baseline and Week 48, an analysis of covariance (ANCOVA) model will be used to analyze continuous endpoints, and a non-parametric ANCOVA model will be used to analyze ordinal outcomes. Baseline value will be included in the model.

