4.1. Changes From Analyses Specified in the Protocol

The following changes were made from analyses specified in the Protocol Amendment (approval dated 27 May 2022):

For exploratory endpoints measured only at Baseline and Week 48, a paired sample t-test or a Wilcoxon Signed-rank test will be used to assess Baseline and Week 48 results for continuous or ordinal outcomes, respectively, in this SAP per Section 7.2.4.

These analyses are to replace the ANCOVA or nonparametric ANCOVA models mentioned in Protocol Amendment 5 (approval date 27 May 2023) Section 9.4.1.1 for these endpoints.

4.2. Changes From Analyses Specified in the Previous Version of the Statistical Analysis Plan

The following updates have been made to the SAP version 1.0 approved on 16 Dec 2022:

Section No. and Name	Description of Change	Justifications
Section 3. Table 1. List of Abbreviations and Definitions of Terms	Added the following abbreviations: 
 • cNCC for calculated non-ceruloplasmin-bound Cu • dNCC for directly measured non-ceruloplasmin-bound Cu • AUEC_{0-48W} for daily mean AUEC of dNCC from 0 to 48 weeks • FIB-4 for Fibrosis-4 • PT for Preferred Term • ULOQ for upper limit of quantification 	To align with Protocol Amendment 5
Section 4. Description of the Protocol	Clarified that a liver biopsy is needed for patients entering Extension Period on Week 48 Clarified that all biopsy samples will be reviewed and scored by an independent expert hepatopathologist blinded to identity and biopsy order	To align with Protocol Amendment 5
Section 4.1. Changes From Analyses Specified in the Protocol	Added statements that ANCOVA or nonparametric ANCOVA models are replaced with a paired sample t-test or a Wilcoxon signed-rank test for continuous exploratory endpoints or ordinal exploratory endpoints tested only at Baseline and Week 48	To align with executed analysis and learnings for this study
Section 4.2. Changes From Analyses Specified in the Previous Version of the Statistical Analysis Plan	Provided summary of changes made in this SAP relative to SAP version 1.0 (approval date 16 Dec 2022)	Good documentation practice

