9.5. Additional Details on Statistical Methods

The reference SAS codes used for efficacy analyses are as follows:

Multiple Imputation

Step 1:

```
proc mi data=xxx nimpute=20 seed=54321 out=yyy;  
  mcmc impute=monotone;  
  var BASE W48;  
run;
```

Step 2:

```
proc ttest data=xxx;  
  by _imputation_;  
  paired BASE*W48;  
run;
```

Step 3:

```
proc mianalyze data=xxx;  
  by AVISIT;  
  modeleffects ESTIMATE;  
  stderr STDERR;  
run;
```

Paired sample t-test

```
proc ttest data=xxx;  
  paired BASE*W48;  
run;
```

Wilcoxon Signed-rank test

```
proc univariate data=xxx;  
  var CHG;  
run;
```

MMRM

```
proc mixed data=xxx method=reml;  
  class AVISITN USUBJID;  
  model CHG=AVISITN BASE / solution ddfm=kr cl;  
  repeated AVISITN / subject=USUBJID type=UN;  
  lsmeans AVISITN / cl;  
run;
```

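### In this single-arm trial the MMRM tests mean change against zero with Baseline as a covariate, so its standard error is too small whenever change depends on Baseline

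*SAP*

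**What the plan says.** SAP 7.2.2 sets the model for CGI-S: "In the MMRM model, the response variables will be change from Baseline", and "Visit and Baseline values will be used as covariates". On covariance and degrees of freedom it says: "An unstructured covariance matrix will be used to model the within-subject error and the Kenward-Roger approximation will be used to estimate the degrees of freedom". From this model "the comparison of post-baseline versus Baseline time points will be tested using a 2-sided test" at the 0.05 level, and the least squares mean change is reported with its SE and 95% CI. Histology and CGI-I are only summarised, so CGI-S is the one secondary efficacy endpoint with a formal test.

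The code in SAP 9.5 is "model CHG=AVISITN BASE / solution ddfm=kr cl", followed by a default LSMEANS statement for visit.

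SAP 7.2.4 applies the same model to MELD, modified Nazer, the plasma copper measures, ceruloplasmin, the quality-of-life scales, BPRS-24, FIB-4 and 24-hour urine. For the plasma copper and ceruloplasmin measures it adds a second MMRM on percent change. Protocol 9.4.1.1 has the same terms: "Fixed-effect terms will include visit and baseline value as covariates". SAP 7.2 sets the criterion: "A 2-sided Type I error rate of 0.05 will be used to define statistical significance for all endpoints", without multiplicity adjustment.

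For exploratory endpoints measured only at Baseline and Week 48, SAP 4.1 moves to a paired t-test or a signed-rank test: "These analyses are to replace the ANCOVA or nonparametric ANCOVA models mentioned in Protocol Amendment 5". The primary liver copper analysis is also a paired t-test.

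**The concern.** Adjusting for Baseline gains precision when two arms are compared, because the Baseline means of the arms largely cancel. Here nothing cancels. The quantity tested is one arm's mean change, and the model reports it at the observed Baseline mean as if that were the population mean. Variation that belongs in the standard error is left out.

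At stake are the only formal secondary efficacy test and the intervals and p-values for the exploratory repeated measures. The SAP would also answer the same one-sample question in two ways: with a correct standard error for endpoints measured twice, and with an understated one, whenever change depends on Baseline, for endpoints measured more often.

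**Working it through.** **Inputs.** From the documents: one arm; response CHG; terms visit and BASE with a common slope; default LSMEANS; two-sided 0.05; 24 evaluable of about 28 enrolled; five post-baseline CGI-S visits (Weeks 4, 12, 24, 36 and 48 in the Schedule of Activities). Not in the documents, so assumed and varied: the Baseline to post-baseline correlation rho, and the ratio k = s1/s0 of post-baseline to Baseline SD.

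**The plan's own figure.** The documents give no operating characteristic for the MMRM beyond its nominal 0.05. Their one power figure concerns the primary paired t-test. With n = 24, reduction 228, SD 319 and one-sided 0.025, the noncentral t gives 91.8%, which agrees with the stated 92%.

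**Algebra at one visit, complete data.**

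1. The least squares mean at the sample mean Baseline equals the raw mean change.
2. The variance the model reports is s1²(1 − rho²)/n.
3. The actual variance of the mean change is (s0² + s1² − 2·rho·s0·s1)/n.
4. The difference is (rho·k − 1)²·s0²/n. This is (slope of change on Baseline)² × Var(sample mean Baseline).
5. With k = 1 the ratio of reported to correct SE is sqrt((1 − rho²)/(2(1 − rho))) = sqrt((1 + rho)/2).
6. The actual two-sided level is about 2·(1 − Φ(1.96 × ratio)).

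Example, k = 1 and rho = 0.5: ratio = sqrt(0.75) = 0.866; 1.96 × 0.866 = 1.697; level about 9.0%.

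Example, k = 0.75 and rho = 0.5 (s0 = 1): reported 0.5625 × 0.75 = 0.422; actual 1 + 0.5625 − 0.75 = 0.8125; ratio = sqrt(0.519) = 0.721; level 15.8%.

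Example, k = 1.25 and rho = 0.8: rho·k = 1, so the slope is zero, the ratio is 1 and the level is 5.0%.

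| rho | SE ratio, k = 1 | Level, k = 1 | Level, k = 0.75 | Level, k = 1.25 |
|---|---|---|---|---|
| 0.3 | 0.806 | 11.4% | 18.4% | 8.3% |
| 0.5 | 0.866 | 9.0% | 15.8% | 6.4% |
| 0.7 | 0.922 | 7.1% | 14.3% | 5.2% |
| 0.8 | 0.949 | 6.3% | 14.3% | 5.0% |
| 0.9 | 0.975 | 5.6% | – | – |

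**Simulation of the repeated-measures model.** REML, unstructured covariance, common slope, five visits, no true change, equal SDs, 6,000 runs per case. A t reference with n − 1 df stood in for Kenward-Roger.

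| rho | n = 24 | n = 28 |
|---|---|---|
| 0.3 | 10.8% | 11.1% |
| 0.5 | 8.4% | 8.0% |
| 0.7 | 6.5% | 6.7% |
| 0.8 | 6.4% | 6.1% |

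At n = 24 and rho = 0.5 the mean reported SE was 0.174, against an actual SD of the estimate of 0.202.

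**Checks on the conditions.**

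- Scores rounded to the 1-7 scale, n = 24: 9.1% at rho 0.5 and 6.0% at rho 0.8.
- 15% dropout, n = 28, rho 0.5 (500 runs): 8.8% with BASE and 4.8% without. The two estimates differed by 0.013 SD on average, so the estimate is exactly unchanged only with complete data.
- Unadjusted test on the same complete data: 4.5-5.4% with normal data, 4.7-5.6% with rounded scores.
- Single-visit simulation, n = 26, equal SDs, rho 0.3, 0.5, 0.7, 0.8 and 0.9: 10.7%, 8.3%, 7.0%, 6.1% and 5.3%. With k = 0.75 it gave 13-18% and with k = 1.25 it gave 5-8%.

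The percent-change MMRMs were not simulated. The omitted term has the same form there, with the slope of percent change on Baseline, but the equal-SD formula does not apply.

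**The case against.** The strongest reply is that the SE is valid conditionally on the observed Baseline mean, which is the usual reading of LSMEANS with a fixed covariate. That is true of the SE but does not rescue the test. If the population mean does not change, the expected change given the sample Baseline mean is (rho·k − 1) × (sample mean − population mean). That is non-zero whenever the two means differ and the slope is not zero. The null of zero change is therefore a statement about the population, and the SAP nowhere restricts it. Kenward-Roger does not help: it allows for estimated covariance parameters, not for a random covariate mean.

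Several other points stand and limit the concern:

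- The primary test does not use this model. The affected p-values are nominal and supportive, in a small open-label study with no multiplicity control.
- Observed change is summarised at each visit with n, mean and SD, so a reader can derive the unadjusted SE. That mitigates the problem without correcting the reported p-value.
- The simulations replaced Kenward-Roger with a t reference. The algebra does not depend on that choice.

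A reader might infer a fixed error rate, such as 6-11%, as a property of this plan. The documents give no correlation or SD ratio for any of these endpoints, so no single range can be claimed, and it is not shown that every listed endpoint is affected. A reader might also take SAP 4.1 as evidence that the sponsor had recognised this defect. SAP 4.2 gives only alignment with executed analysis and learnings from the study as the reason. Finally, testing five visits raises the chance of some significant result even with correct standard errors. That is a separate matter of multiplicity.

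**Conclusion.** Wrong as written, and it should be fixed. For CGI-S and the exploratory repeated measures, the reported SE leaves out (slope of change on Baseline)² × Var(sample mean Baseline), and nothing in either document restores it.

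The size is conditional. With equal SDs, the nominal 5% test runs at about 11% for rho 0.3, 8-9% for 0.5, 7% for 0.7 and 5.5% for 0.9. With a post-baseline SD 0.75 of the Baseline SD it is about 13-18%; with 1.25 times, about 5-8%. If change is unrelated to Baseline there is no inflation. These figures rest on assumed values of rho and k and, for the algebra, on complete data.

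It would go too far to read this as a threat to the primary conclusion. The paired t-test on liver copper carries no Baseline covariate and is untouched.

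**What to change.** In SAP 7.2.2, 7.2.4 and 9.5, drop BASE from both kinds of model: `CHG=AVISITN` for change, and percent change on `AVISITN` for the percent-change models. Keep the same REPEATED statement and Kenward-Roger.

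For absolute change only, an acceptable alternative is to put Baseline in the response vector as a further visit level, under unstructured covariance, and test each visit minus Baseline. This uses the Baseline information when visits are missing. It cannot serve percent change, which is identically zero at Baseline. It should be tied to the unstructured matrix, because under a simpler fallback structure the SE of change would depend on that structure's Baseline-to-visit correlation.

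Protocol 9.4.1.1 specifies the covariate, so list the departure in SAP 4.1.

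The cost is a few lines of wording and code. With equal SDs, intervals widen to their correct width by about 24% at rho 0.3 (1/0.806) and 3% at rho 0.9 (1/0.975). The response-vector form adds one row to the covariance matrix: 15 to 21 parameters for CGI-S with five post-baseline visits, and 36 to 45 for plasma endpoints with eight, from about 24-28 patients.
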